Procedure. The current of taVNS was applied bilaterally from the tragus and turbinate parts of the ear with the VagustimTM device. The current frequency used in modulation mode is 10 Hz, and the pulse width was 300 μ s (In modulation mode, the pulse rate and width are automatically changed in a loop pattern. The pulse width was reduced by 50% from its original setting in 0.5 seconds; then, the pulse rate was changed in 0.5 seconds, reduced by 50% from the original setting. Total cycle time is 1 second.). The current intensity was applied for 5 minutes, keeping the current constant where the participant felt comfortable. Sham applications were applied using a current-free headset specifically designed for this purpose. Participants observed the device's functionality but supplied no current.

Measures.

Numerical Rating Scale (NRS). Data was queried separately for lower abdominal, waist, and bilateral thigh pain. Participants were required to complete an NRS questionnaire through the Google Forms web survey platform (Google LLC, Mountain View, CA, USA) before bed at

night on days 1, 2, and 3 of two consecutive menstrual cycles. The questionnaire was based on the most severe pain they experienced during the day. The minimum score of the NRS is 0, and the maximum score is 10. Higher scores are associated with more severe pain intensity.

Pressure Pain Threshold (PPT). Fabrication Enterprises, Inc., used a Push-Pull Force Gauge® (1200-304) to measure the pressure pain threshold. This handheld algometer allows linear force application ranging between 0 and 10 kg (22 lb × ¼ lb and 10 kg × 100 g). Initially, two exercises were performed on the dominant forearm's extensor muscles to familiarize patients with the equipment. The evaluator positioned the algometer perpendicular to each point and applied gradual pressure at a constant rate of approximately 0.5 kg/cm²/s. The pressure was increased until the participant reported feeling pain. Each point was evaluated three times, and the average value was recorded. The measurement was performed on five reference points in the abdomen and one reference point in the lumbar spine, as in a previous study where pain was evaluated in PD.

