IBM SPSS version 28.0 software (IBM Corp., Armonk, NY, USA) was utilised for statistical analysis. Before the statistical analysis, the Shapiro-Wilk normality test was used to assess data distribution because of $n < 50$. Demographic data and clinical baseline variables were compared among the 2 groups by independent samples t-test for continuous variables and a χ^2 test for categorical variables. Continuous variables were expressed as mean \pm standard deviation (SD), while categorical variables were reported as number and frequency. The independent and paired samples t-test was compared to normally distributed variables between two groups. Two-way analysis of variance (ANOVA) was used for multiple comparisons of normally distributed

variables. The effects of stimulation on pain, pressure pain threshold, menstrual symptoms, and physical performance were calculated using a mixed ANOVA, where the dependent variables were pain, pressure pain threshold, menstrual symptom, and physical performance score, and the independent fixed variables were time, stimulation group (taVNS and sham), and interaction term was group vs time. Post hoc comparisons were carried out when appropriate using Bonferroni correction for multiple comparisons. Greenhouse-Geisser correction was applied when the assumption of sphericity was violated. In the F tests, partial eta squared (η^2) was used as an effect size indicator, elucidated as small, 0.01; medium, 0.06; and large, 0.14. In the t-tests, Cohen's d (d) was used as an effect size indicator, elucidated as small, 0.2; medium, 0.5; large, 0.8. A p value of <0.05 was considered statistically significant.

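### The t-tests and two-way ANOVA apply only to variables that pass Shapiro-Wilk, with no fallback, so HAM-A, both PANAS scores and possibly FEMD may have no stated treatment comparison

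*Combined protocol and SAP*

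**What the plan says.** All the relevant text is in the Statistical Analysis Plan section of the combined document.

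- **Preliminary check.** Ahead of the analysis, "the Shapiro-Wilk normality test was used to assess data distribution because of" a sample below 50. No significance level is given for this check. Nor does the plan say whether it is applied by arm, by time point, to changes or to residuals, or what follows from a failure.
- **Tests tied to normality.** "The independent and paired samples t-test was compared to normally distributed variables between two groups". The next sentence adds: "Two-way analysis of variance (ANOVA) was used for multiple comparisons of normally distributed" variables.
- **Test not tied to normality.** "The effects of stimulation on pain, pressure pain threshold, menstrual symptoms, and physical performance were calculated using a mixed ANOVA", with time, group and their interaction as terms.
- **Other unconditional items.** Baseline variables are compared "by independent samples t-test for continuous variables and a χ^2 test for categorical variables". Summaries are also unconditional: "Continuous variables were expressed as mean" and SD.

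No rank test, transformation, bootstrap or other route for a non-normal variable appears anywhere in the document. The Measures section also lists HAM-A (0–56), PANAS positive and negative affect (10–50 each) and FEMD (14–70). HAM-A and PANAS are not among the four domains given to the mixed ANOVA. FEMD is there only if menstrual symptoms is meant to include it.

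**The concern.** A plan should fix the test for each outcome before the data are seen. Here, for any outcome without the mixed ANOVA, the only tests of a treatment effect or a pre–post change are those that require normality. If such an outcome fails the check, the plan gives no analysis. The analyst must then invent one, ignore the gate or leave the outcome untested, and all three are decisions made with the outcome data in view.

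The missing significance level and unit of testing add a second layer of choice. The same score can pass when pooled and fail in one arm, or pass at baseline and fail at post-test.

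This reaches a stated aim. The Objectives section names functional and emotional symptoms alongside pain and physical performance. HAM-A and PANAS are the anxiety and affect measures, and FEMD is the instrument that measures functional and emotional impact.

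**Working it through.** The plan states no sample size, power or expected failure rate, so there is no figure of its own to reproduce. The check has four steps.

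**1. Which outcomes keep an ungated test.** Counting from the Measures section:

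| Domain | Outcomes | Mixed ANOVA without a normality condition? |
|---|---|---|
| Pain (NRS: abdomen, waist, thighs) | 3 | Yes |
| Pressure pain threshold (5 abdominal points, 1 lumbar) | 6 | Yes |
| MSQ | 1 | Yes (menstrual symptoms) |
| 6MWT | 1 | Yes (physical performance) |
| FEMD | 1 | Unclear |
| HAM-A | 1 | No |
| PANAS positive, negative | 2 | No |

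The total is 3 + 6 + 1 + 1 + 1 + 1 + 2 = 15. Of these, 3 + 6 + 1 + 1 = 11 keep a stated test whatever Shapiro-Wilk shows. Four are exposed, or three if FEMD counts as a menstrual symptom. The unconditional baseline t-test covers the exposed scores too, but it says nothing about treatment effect.

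**2. How often the gate would fail on normal data.** Assumptions: Shapiro-Wilk at 0.05 (the plan gives no level), exactly normal data, independent checks. The chance of at least one failure in k checks is 1 − 0.95^k.

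| Checks per score | Four scores (FEMD exposed) | Three scores (FEMD covered) |
|---|---|---|
| Once | k = 4: 1 − 0.8145 = 18.6% | k = 3: 1 − 0.8574 = 14.3% |
| In two arms, or at two times | k = 8: 1 − 0.6634 = 33.7% | k = 6: 1 − 0.7351 = 26.5% |
| Two arms by two times | k = 16: 1 − 0.4401 = 56.0% | k = 12: 1 − 0.5404 = 46.0% |

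The scores are probably positively correlated, which would lower these figures. Under complete dependence the chance would be 5%.

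**3. How often it would fail on skewed data.** A 0–56 integer score was simulated as a rounded gamma variable (shape 2, scale 5; 4,000 samples per size). Shapiro-Wilk at 0.05 rejected in about 25% of samples at n = 10, 53% at n = 20, 66% at n = 24 and 95% at n = 49. Here n is the size of whatever sample is tested. The plan tells us only that n is below 50, and the shape of the distribution is an assumption.

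**4. Whether the gate is needed.** Scores on a 0–10 integer scale were simulated from a normal distribution with mean 2 and SD 2.5, rounded and clipped, so that many values sit at the floor. With no true difference between arms, the two-sample t-test rejected in 4.8% to 5.1% of trials at 10, 12 and 20 per arm, against a nominal 5%. Scores shaped like these fail Shapiro-Wilk in about 73% of samples of 20, yet the test they would be denied keeps its error rate.

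**The case against.** The strongest reply is that the plan already names a model for its main outcomes. The mixed ANOVA sentence carries no normality condition, and 11 of 15 outcomes fall under it. That stands, and it rules out several stronger readings:

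- **That the data decide the test for every outcome, or that different pain areas could end up with different tests.** All pain scores are assigned to the mixed ANOVA by name. One ambiguity remains: a group-by-time mixed ANOVA is itself a kind of two-way ANOVA. If the two sentences describe one analysis, the gate would reach the main outcomes too. The text does not say so.
- **That outcomes are very likely to lose their test, because 30 checks (15 outcomes, pre and post) give 1 − 0.95^30 = 79%, or because floor-heavy pain scores often fail.** The arithmetic is right, but most of those checks concern outcomes that keep their mixed ANOVA.
- **That the check is aimed at raw scores when it should be aimed at residuals.** The plan does not state the unit. Checking raw scores within each arm is the same as checking residuals for a two-group t-test.
- **That the choice is made after unblinding, or that a rank test would be substituted.** The document describes neither.

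It is also fair to say that a single sentence naming a test for the exposed scores would close the gap in the narrowest sense. It would still leave the t-tests on the other outcomes appearing or vanishing with the data.

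**Conclusion.** The point holds for the t-tests and two-way ANOVA, and for the outcomes that have nothing else: HAM-A, PANAS positive, PANAS negative, and FEMD if it lies outside menstrual symptoms. For these, whether a comparison is made, and which one, depends on a preliminary test with no stated level, unit or alternative. It does not hold for pain, pressure pain threshold, MSQ or 6MWT as the plan is written.

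A failure is a realistic event: 19% to 56% for four normal scores, depending on how the check is applied, and higher if scores are skewed. These figures rest on an assumed 0.05 level, independence, and sample sizes and shapes that the plan does not give. The harm is an unplanned or missing analysis. The simulation gives no sign that the t-test itself would mislead. The defect should be corrected, but it does not undermine the mixed ANOVA of the main outcomes.

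**What to change.** Delete the Shapiro-Wilk gate. State that every outcome, with HAM-A, both PANAS scores and FEMD listed by name, is analysed by one pre-specified between-arm comparison of the post-test value adjusted for its own baseline value, whatever the raw distribution. Check the residuals of that model and report what was found, without letting the check change the primary test. The design already collects values at both time points, so no new data are needed.

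A permutation p-value or bootstrap confidence interval may be added, provided it is fixed in advance as a sensitivity analysis for all outcomes and is not triggered by a failed check.

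If the mixed ANOVA is kept instead, the minimum change is to extend it without condition to the four scores, and to say whether the two-way ANOVA sentence describes the same model.

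The cost is SAP wording and a little more analysis, plus one extra result per outcome if the sensitivity analysis is added.

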Study Protocol and Statistical Analysis Plan

Title of Study: Effects of Transcutaneous Vagus Nerve Stimulation (taVNS) in Individuals with Primary Dysmenorrhea: A Randomized Controlled Study

NCT Number: NCT06146569

Date of Document: September 18, 2023

Table of contents

	Page number
Study Protocol	3
Objectives	3
Design	3
Methods	3
Statistical Analysis Plan	4

Study Protocol

Objectives:

This study aims to investigate the effects of transcutaneous auricular vagus nerve stimulation (taVNS) on pain, functional and emotional symptoms, and physical performance in individuals with primary dysmenorrhea (PD).

Design:

A small randomized controlled trial design was conducted online at two time points: 1) baseline/pre-test and 2) post-test (one week after pre-test). Data were collected by face-to-face interview method.

Participants will be randomly assigned to one of two conditions: 1) intervention (women received taVNS treatment) or 2) sham (Sham applications were applied using a current-free headset specifically designed for this purpose. Participants observed the device's functionality but supplied no current).

The study was approved by the Artvin Çoruh University Rectorate Scientific Publications Ethics Committee (date: 18/09/2023, procedure number: E-105136) and was by the ethical standards of the World Medical Association (Declaration of Helsinki).

Methods:

Sample and Recruitment. Women who had never given birth before participated in the study. To participate in the research, the following criteria must be met: 1) being diagnosed with PD according to the No. 345 Primary Dysmenorrhea Consensus Guidelines; 2) an NRS score of at least three during menstruation before treatment; 3) being a woman between the ages of 18-40; 4) a regular menstrual cycle of 28 ± 7 days; 5) being nulliparous; 6) no history of brain surgery, tumor, or intracranial metal implantation; 7) No chronic genitourinary infection or alcohol or drug use. Potential participants were invited to study at Artvin Çoruh University through voice announcements and brochures. Following diagnosis with primary dysmenorrhea at Artvin State Hospital, those who met the study's inclusion criteria received treatment at Artvin Çoruh University Physiotherapy Laboratory between November 2023 and January 2024.

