Menstrual Symptom Questionnaire (MSQ). The scale consists of 22 items and uses a 5-point Likert-type format. Participants were asked to rate the severity of their menstrual symptoms on a scale of 1 (never) to 5 (always). The scale contains three subscales: 'Negative Effects/Somatic Complaints' (items 1-13), 'Menstrual Pain Symptoms' (items 14-19), and 'Coping Methods' (items 20-22). The maximum score on the scale is 110, and the minimum score is 22. MSQ score is calculated by taking the average score of all items in the scale. High scores are associated with increased menstrual symptoms.

Functional and Emotional Measure of Dysmenorrhea (FEMD). Scale consisting of 14 items, evaluates dysmenorrhea functionally and emotionally with a 5-point Likert-type item. The reliability and validity study of the scale developed in 2012. As the scores obtained from the scale with a minimum score of 14 and a maximum score of 70 increase, the functional and emotional impact of dysmenorrhea also increases.

Hamilton Anxiety Scale (HAM-A). Patients with chronic pain often experience mood disorders, such as depression and anxiety. The Hamilton Anxiety Scale (HAM-A) was used to assess the intensity of anxiety symptoms. The scale measures both mental and physical anxiety with 14 symptom-defined items. Each item is scored from 0 (not present) to 4 (severe). The total score range is 0-56. On the anxiety scale, scores of 17 or below indicate mild anxiety, while scores of 18-24 indicate moderate anxiety, and scores of 25-30 indicate severe anxiety.

6-Minute Walk Test (6MWT). The 6-Minute Walk Test (6MWT) was evaluated submaximal functional capacity. 6MWT measures the maximum distance participants can walk as quickly as possible for six minutes.

Positive and Negative Affect Schedule (PANAS). For taVNS administration, the positive and negative affect was assessed before and after treatment using the Positive and Negative Affect Schedule (PANAS). This 5-point Likert-type scale was developed in 1988 and includes 20 items: 10 positive and ten negative. A score range of 10-50 assesses both positive and negative effects.

Statistical Analysis Plan

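### HAM-A and PANAS are not named in the SAP's only group-by-time model, and the general t-test sentence they fall to gives no score type and describes a paired test as a between-group comparison

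*Combined protocol and SAP*

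**What the plan says.** The Objectives section says that the trial studies effects "on pain, functional and emotional symptoms, and physical performance in individuals with primary dysmenorrhea (PD"). The Design section describes two parallel arms: "Participants will be randomly assigned to one of two conditions". No matching of participants is described.

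Under Methods, Measures, the protocol lists seven instruments: NRS, PPT, MSQ, FEMD, HAM-A, 6MWT and PANAS. On anxiety it says: "The Hamilton Anxiety Scale (HAM-A) was used to assess the intensity of anxiety symptoms".

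The Statistical Analysis Plan has one sentence on how treatment effects are obtained: "The effects of stimulation on pain, pressure pain threshold, menstrual symptoms, and physical performance were calculated using a mixed ANOVA". The same sentence repeats the outcome list: "the dependent variables were pain, pressure pain threshold, menstrual symptom, and physical performance score". The model terms are time, group and their interaction.

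Two general sentences come before it. One is "The independent and paired samples t-test was compared to normally distributed variables between two groups". The other begins "Two-way analysis of variance (ANOVA) was used for multiple comparisons of normally distributed" and names neither outcomes nor factors. On multiplicity the SAP says: "Post hoc comparisons were carried out when appropriate using Bonferroni correction for multiple comparisons". The significance level is 0.05, and no rule states which result would count as a taVNS effect.

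**The concern.** A reader cannot tell from the SAP which test decides whether taVNS changed anxiety or affect. HAM-A and PANAS bear on the trial's stated aim if emotional symptoms are read broadly. They are measured, yet the only sentence about effects of stimulation leaves them out.

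The sentence they would fall to has two weaknesses:

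- **Score type.** It does not say whether an independent t-test would use post-test or change scores. That choice affects what a trial with fewer than 50 participants can detect. If left open, it could be made after the results are seen.
- **Paired test.** It presents a paired test as a comparison of two groups. With unmatched randomised arms, a paired test can only assess change within one arm. A result that is significant under taVNS and not significant under sham is not evidence that the arms differ, and the SAP does not rule out that inference for these scales.

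**Working it through.** **Matching measures to analyses**

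| Measure | Named in the group-by-time model? |
|---|---|
| NRS | Yes, as pain |
| PPT | Yes |
| MSQ | Yes, as menstrual symptom |
| 6MWT | Yes, as physical performance |
| FEMD | Not by name; probably under menstrual symptom |
| HAM-A | No |
| PANAS positive, PANAS negative | No |

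The baseline comparison by independent t-test is not an analysis of effect. That leaves HAM-A and PANAS with the general t-test and two-way ANOVA sentences. Both are limited to normally distributed variables, and neither names an outcome.

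**How much the score type matters (illustration)**

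The SAP gives no target sample size, SD or pre-post correlation, so there is no planned figure to reproduce. Assumptions: the SAP's n < 50 is read as the total, with 20 per arm; two-sided 0.05; 80% power; correlation r of 0.3, 0.5 or 0.7.

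*Post-test t-test.* The detectable difference d (in SD of the score) is the value at which a t-test with 2n − 2 degrees of freedom and noncentrality d√(n/2) has 80% power. At n = 20 per arm, d = 0.91. At 10, 15 and 24 per arm it is 1.32, 1.06 and 0.83.

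*Change score.* Multiply by √(2(1 − r)). With two time points, the group-by-time F is the square of the independent t on change scores, so this line also describes the mixed ANOVA.
- r = 0.3: 0.91 × √1.40 = 1.08
- r = 0.5: 0.91 × √1.00 = 0.91
- r = 0.7: 0.91 × √0.60 = 0.70

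*Baseline-adjusted (ANCOVA).* Multiply by √(1 − r²); the one lost degree of freedom makes little difference here.
- r = 0.3: 0.91 × √0.91 = 0.87
- r = 0.5: 0.91 × √0.75 = 0.79
- r = 0.7: 0.91 × √0.51 = 0.65

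The ordering does not depend on 20 per arm. The factor 1 − r² never exceeds 1, and 2(1 − r) − (1 − r²) = (1 − r)², which is never negative.

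**What separate paired tests could produce (illustration of a practice the SAP does not state)**

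Assume the same true change in both arms, expressed as dz in SD of the change score. The rate of finding taVNS significantly improved and sham not significant is P(taVNS significant, improving) × P(sham not significant), from the noncentral t with n − 1 degrees of freedom.

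- dz = 0: 0.025 × 0.95 = 2.4%
- dz = 0.2, n = 20: 0.1335 × (1 − 0.1360) = 11.5%; with each paired test at 0.025 (Bonferroni over two), 0.0801 × (1 − 0.0811) = 7.4%
- dz = 0.45, n = 20: 0.4803 × (1 − 0.4803) = 25.0%; at 0.025, 0.3590 × (1 − 0.3590) = 23.0%
- dz = 1.0, n = 24: 0.9968 × (1 − 0.9968) = 0.3%

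The group-by-time test gives 2.5% in the taVNS direction throughout. Over 10 to 24 per arm, the unadjusted paired rate is 4–13% at dz of 0.1–0.2, 12–25% at 0.3–0.6 and 0.3–16% at 1.0.

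**The case against.** The strongest reply is that little is actually missing.

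- **FEMD.** The objective and the model's outcome list run in parallel, and menstrual symptoms stand where functional and emotional symptoms stood. FEMD is a dysmenorrhea scale. This stands: FEMD is probably covered, and the SAP need only say so.
- **A between-arm test exists.** A reader might infer that HAM-A and PANAS have no between-arm analysis at all. The documents do not support that. The general sentence includes an independent t-test, and comparing post-test scores between randomised arms is valid. What remains is that the scales are not named and the score type is open.
- **The paired wording.** The sentence is loosely written throughout. Its likely meaning is independent tests between arms and paired tests within them. This is probably right, but the text as it stands is still incorrect.
- **No stated misuse.** A reader might infer that taVNS effects will be claimed from paired tests. The SAP does not say so, and its one sentence on effects uses a group-by-time interaction. The paired-test rates therefore describe a hypothetical practice.
- **Assumed inputs.** Arm size, correlation and shared change are all assumed, and some of the resulting paired-test rates lie below the 2.5% of the correct test. This stands: they do not show that the effect is important in this trial.

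The reply does not remove two points. Baseline adjustment is a specific, more precise method than the unadjusted t-test now stated, and the t-test sentence needs correcting.

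**Conclusion.** The point holds as a minor one. HAM-A and PANAS are measured but not named in the SAP's only group-by-time model. The general t-test sentence they fall to leaves the score type open and misdescribes a paired test.

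The gain from baseline adjustment is modest against a post-test t-test at r = 0.3 (0.87 against 0.91 SD) and larger at r = 0.7 (0.65 against 0.91 SD). Against change scores the order reverses: 0.87 against 1.08 SD at r = 0.3, and 0.65 against 0.70 SD at r = 0.7. These figures assume 20 per arm and the stated correlations. The textual gap rests on none of these assumptions.

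The paired-test rates, from 0.3% to 25% depending on shared change and arm size, are not a property of the plan. No primary outcome is named, so nothing shows that these scales carry the main conclusion.

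**What to change.** 1. Confirm that PANAS is collected in both arms at both time points, because its entry under Measures ties the assessment to taVNS administration. If it is not, label PANAS descriptive.
2. Analyse HAM-A, PANAS positive and PANAS negative by ANCOVA of the post-test score on arm and baseline score. State whether FEMD belongs to the menstrual-symptom outcome; if it does not, analyse it in the same way.
3. Reword the t-test sentence so that independent tests compare arms and paired tests describe change within an arm.
4. Say whether the two-way ANOVA is the mixed ANOVA and which outcomes it covers.
5. State that taVNS effects are claimed only from the between-arm contrast.

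The cost is SAP wording and slightly more analysis work. No new data are needed if the scales are collected in both arms at both time points. Within-arm p-values would no longer support claims, and these scales would be analysed by a different model from the four outcomes already listed. Adding them to the mixed ANOVA would avoid that difference, but below r = 0.5 it is less precise than a post-test comparison (1.08 against 0.91 SD at r = 0.3).

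### The group × time mixed ANOVA leaves the collected baseline unused as a covariate; at equal SDs, ANCOVA would cut treatment-effect variance by about 21–23% (r = 0.5) or 11–13% (r = 0.7)

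*Combined protocol and SAP*

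**What the plan says.** The Statistical Analysis Plan section assesses stimulation effects with a mixed ANOVA in which "the independent fixed variables were time, stimulation group (taVNS and sham), and interaction term was group vs time". The same sentence lists the outcomes this model covers: "where the dependent variables were pain, pressure pain threshold, menstrual symptom, and physical performance score". Baseline variables are otherwise used only for between-group comparison by t-test or chi-square. No ANCOVA or other baseline adjustment appears anywhere.

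The Design section places measurement "at two time points: 1) baseline/pre-test and 2) post-test". Three kinds of outcome in the mixed-ANOVA list then have one value before and one after treatment:

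- **MSQ:** "MSQ score is calculated by taking the average score of all items in the scale".
- **PPT:** "Each point was evaluated three times, and the average value was recorded".
- **6MWT:** a single distance.

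Pain on the NRS is different. It is recorded at "night on days 1, 2, and 3 of two consecutive menstrual cycles", so it has no single pre and post value until a summary is chosen. FEMD, HAM-A and PANAS are not named in the mixed-ANOVA list and lie outside this point.

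**The concern.** With two time levels, the group × time interaction compares mean change between arms. A change score subtracts the whole baseline value, which is the same as assuming a pre-post slope of exactly 1. When the true slope is lower, the subtraction adds baseline noise to the treatment contrast. ANCOVA estimates the slope from the data and removes that noise.

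The issue is precision, not bias. It matters because the trial is small and the documents contain no sample-size calculation, so no stated power margin absorbs the loss. Under most of the conditions examined below, the planned test is more likely to miss a real taVNS effect than an adjusted test on the same data.

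**Working it through.** **Inputs**

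- From the documents: two arms, randomised; pre and post measurement; significance at 0.05; n < 50. If n is the total and allocation is 1:1 (assumed), there are at most 24 per arm.
- Assumed, because the documents are silent: n = 12 or 20 per arm; pre-post correlation r from 0.3 to 0.9; k = SD_pre/SD_post from 0.8 to 1.25; two-sided testing; for power, an effect d = 0.8 in post-SD units.
- The plan states no figure to reproduce.

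**Step 1: the planned test is a change-score test.** On one simulated data set with 12 per arm, the interaction F and the squared t on change scores were both 0.0555.

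**Step 2: variances, with SD_post = 1**

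- Change score: (1 + k² − 2rk)(2/n), with 2n − 2 degrees of freedom.
- ANCOVA: (1 − r²)(2/n)[1 + 1/(2n − 4)], with 2n − 3 degrees of freedom. The bracket is the expected cost of estimating the slope: 1.028 at n = 20 and 1.050 at n = 12.

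**Step 3: the loss is capped.** Since 1 + k² − 2rk = (1 − r²) + (k − r)², the change score carries an extra (k − r)² that is never negative. ANCOVA can therefore lose at most 1/(2n − 4), which is 1/36 = 2.8% at n = 20 and 1/20 = 5.0% at n = 12. The cap is reached only at r = k.

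**Step 4: headline cases, k = 1**

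- r = 0.5: the change-score factor is 1 + 1 − 1 = 1.00. ANCOVA is 0.75 × 1.028 = 0.771 (n = 20) or 0.75 × 1.050 = 0.7875 (n = 12). Cut: 22.9% or 21.2%.
- r = 0.7: the change-score factor is 2 − 1.4 = 0.60. ANCOVA is 0.51 × 1.028 = 0.524 or 0.51 × 1.050 = 0.5355. Cut: 12.6% or 10.8%.

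Simulation with 200,000 trials per cell gave 23.0% and 21.4% at r = 0.5, and 12.7% and 10.9% at r = 0.7.

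**Step 5: full range.** Variance cut in percent, n = 20 / n = 12; a negative value means ANCOVA is worse.

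| k | r = 0.3 | r = 0.5 | r = 0.7 | r = 0.8 | r = 0.9 |
|---|---|---|---|---|---|
| 0.8 | 19.4 / 17.6 | 8.2 / 6.2 | −0.8 / −3.0 | −2.8 / −5.0 | 2.4 / 0.3 |
| 0.9 | 26.4 / 24.8 | 15.3 / 13.5 | 4.7 / 2.6 | 0.0 / −2.2 | −2.8 / −5.0 |
| 1 | 33.2 / 31.7 | 22.9 / 21.2 | 12.6 / 10.8 | 7.5 / 5.5 | 2.4 / 0.3 |
| 1.1 | 39.7 / 38.4 | 30.6 / 29.1 | 21.8 / 20.1 | 17.8 / 16.0 | 15.1 / 13.3 |
| 1.25 | 48.4 / 47.3 | 41.3 / 40.0 | 35.5 / 34.1 | 34.2 / 32.8 | 37.5 / 36.2 |

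ANCOVA is worse only when r is close to k. At k = 0.8 that is r from 0.68 to 0.88 (n = 20) or 0.63 to 0.90 (n = 12). At k = 1 it is r above 0.946 or above 0.905. At k = 1.1 or 1.25 it never happens.

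**Step 6: power, by noncentral t, with ANCOVA averaged over chance baseline imbalance.** For k = 1, r = 0.5, n = 20, the noncentrality is 0.8/√(1.00 × 0.1) = 2.53 for change scores and about 0.8/√(0.771 × 0.1) = 2.88 for ANCOVA.

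| n per arm, r = 0.5 | Change, k = 0.8 | Change, k = 1 | Change, k = 1.25 | ANCOVA |
|---|---|---|---|---|
| 20 | 77% | 69% | 58% | 80% |
| 12 | 53% | 47% | 37% | 56% |

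Gains shrink as r rises. At k = 1 and n = 20, power goes from 88.9% to 92.5% at r = 0.7, from 97.4% to 98.1% at r = 0.8, and does not change at r = 0.9. The largest loss in the grid at d = 0.8 is 87.7% to 86.0% (n = 12, k = 0.8, r = 0.8).

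**Step 7: NRS.** The entry rule, "an NRS score of at least three during menstruation before treatment", could lower k for pain. For assumed unselected means of 5–7 and SDs of 1.5–2.5, removing scores below 3 shrinks the baseline SD to 0.80–0.99 of its unselected value. No such limit is set on MSQ, PPT or 6MWT. In an illustration with 3-day means (n = 20, d = 0.5 on each post day, all correlations 0.5, equal SDs), power is 76% for the change score and 80% for ANCOVA.

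**The case against.** The planned analysis is a coherent, unbiased test of the stated objective, and the size of any gain depends wholly on values the documents do not give. In the grid above, 13 of 50 entries show a gain under 3%. Of the 18 entries with k ≤ 1 and r ≥ 0.7, 13 gain under 3%, 7 of those are losses and one is exactly zero. A short interval between tests and triplicate PPT readings could push r up. The worst power loss also depends on d: at d = 0.5, n = 12, k = 0.9, r = 0.9, power falls from about 77% to 74%. All of this stands, and it limits how much to promise. It does not reverse the choice, because the loss cap holds for every r and k.

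The Greenhouse-Geisser provision suggests that some model has more than two within-subject levels, and the plan does not say whether PPT point is a factor. The multi-day NRS is enough to explain that provision, but the two-level reading of PPT is an interpretation. Testing six PPT points as well as MSQ, 6MWT and the NRS sites raises multiplicity, though equally so under the planned tests. ANCOVA also assumes a linear, common slope, which is hard to check at about 12 per arm.

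Finally, treatment is described in the past tense as given "between November 2023 and January 2024", so the analysis may already be fixed. That limits the status of an ANCOVA, not its usefulness.

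**Conclusion.** The concern holds as a point of efficiency that should be addressed. For MSQ, 6MWT and PPT at each point, the plan forgoes an inexpensive gain in precision. The gain is 21–23% of variance at r = 0.5 and 11–13% at r = 0.7, if pre and post SDs are equal and there are 12–20 per arm. It is larger when the baseline SD exceeds the post SD, and small or slightly negative when r is close to SD_pre/SD_post. The trade is lopsided: tens of percent to gain, against an expected loss of at most about 3% (20 per arm) or 5% (12 per arm). Confidence in the size is medium, since r, the SDs, the effect size and the number per arm are all assumed. The direction of the advice does not depend on them.

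**What to change.** For each mixed-ANOVA outcome with one pre and one post value (MSQ score, 6MWT distance, each PPT point), replace the group × time test with ANCOVA: post-treatment value on group, with that outcome's own baseline as covariate. Report the adjusted mean difference with its 95% CI, and base the efficacy conclusion for that outcome on that contrast.

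For NRS, apply the same model to a stated per-cycle summary, for example the 3-day mean at each site. Choosing that summary is a separate matter; once it is fixed, the covariate adds only a little.

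The cost is a change of SAP wording and one degree of freedom, with the same data and software, plus the small possible loss of precision given above. If unblinded results have been seen, keep the planned analysis and report the ANCOVA beside it, labelled post hoc.
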